8.1.1 Adverse Events Categorisation, Recording, and Follow-up

Investigators must carefully monitor patients for the occurrence of AEs, including clinical laboratory, vital signs and ECG variables. Assessments must be made of the seriousness, severity and relationship to the administration of study treatment (causality). These assessments must be made by the Investigator or delegated to an appropriately trained and experienced physician. The Investigator must promptly record all identified AEs in the eCRF and patient medical notes.

The Investigator should report a diagnosis or a syndrome rather than individual signs or symptoms, wherever possible. The Investigator should also try to separate a primary AE considered as the foremost untoward medical occurrence from secondary AEs which occurred as complications.

During and following a patient's participation in this study, the Investigator must ensure that adequate medical care is provided to a patient for any AEs, including clinically significant laboratory values, related to the trial.

8.1.1.1 Severity of Adverse Events

Adverse events will be classified by the Investigator according to the following criteria:

- Mild (Grade 1 Common Terminology Criteria for Adverse Events [CTCAE]): Asymptomatic or mild symptoms; clinical or diagnostic observations only; intervention not indicated.
- Moderate (Grade 2 CTCAE): Minimal, local or noninvasive intervention indicated; limiting age-appropriate instrumental Activities of Daily Living (ADL). Instrumental ADL refers to preparing meals, shopping for groceries or clothes, using the telephone, managing money, etc.
- Severe (≥ Grade 3 CTCAE): Severe or medically significant but not immediately life-threatening; hospitalization or prolongation of hospitalization indicated; disabling, limiting self care ADL. Self care ADL refers to bathing, dressing and undressing, feeding self, using the toilet, taking medications, and not bedridden. Life-threatening consequences; urgent intervention indicated; Death related to AE.

Changes in the severity of an AE should be documented to allow an assessment of the duration of the event at each level of severity to be performed. Adverse events characterised as intermittent require documentation of onset and duration of each episode.

8.1.1.2 Causality of Adverse Events

The relationship of an AE to IMP administration will be classified by the Investigator according to the following:

- Related: The temporal relationship of the AE to IMP administration makes a causal relationship possible, and other medications, therapeutic interventions, or underlying conditions do not provide a sufficient explanation for the observed event.
- Not related: The temporal relationship of the AE to IMP administration makes a causal relationship unlikely or remote, and other medications, therapeutic interventions, or underlying conditions provide a sufficient explanation for the observed event.

As this is a double-blind study, the causality assessment should be made under the assumption that the patient is receiving active study treatment. If considering unblinding, this assessment should be made prior to unblinding to avoid bias.

8.1.1.3 Follow-up of Adverse Events

During the study, all AEs will be proactively followed up for each patient. Every effort should be made to obtain a resolution for all events, even if the events continue after the patient discontinued the study.

Any AEs already recorded and designated as "continuing" should be reviewed at each subsequent assessment for their final outcome.

For any AE which remains unresolved after completion of the trial, detailed evaluation and follow-up should be attempted until the AE has been resolved or a reasonable explanation for its persistence is found.

1-Mar-2022

Version number: 1

8.1.2 Serious Adverse Event Assessment and Reporting to Sponsor

The Investigator must pursue and obtain information adequate both to determine the outcome of the AE and to assess whether it meets criteria for classification as a SAE requiring immediate notification to the Sponsor (or designee).

A SAE is any AE that:

- Results in death.
- Is life-threatening (ie, in the opinion of the Investigator, the patient is at immediate risk of death from the AE).
- Results in inpatient hospitalisation or prolongation of existing hospitalisation (hospitalisation is defined as an inpatient admission, regardless of length of stay; hospital admissions for procedures planned before administration of IMP do not need to be reported).
- Hospitalisation or prolongation of hospitalisation in the absence of a precipitating AE is not in itself an SAE. Examples include:
 - o Social admission (eg, patient has no place to sleep);
 - o Protocol-specified admission during a clinical study (eg, for a procedure required by the study protocol);
 - Optional admission not associated with a precipitating AE (eg, for elective cosmetic surgery);
 - Surgery that was planned prior to study enrolment (appropriate documentation is required for these cases) and was not caused by worsening of a pre-existing condition.
- Results in a persistent or significant disability/incapacity, where disability is a substantial disruption of a person's ability to conduct normal life functions.
- Results in congenital anomaly/birth defect in the offspring of a patient who received the IMP.
- Constitutes an important medical event that may not result in death, be life-threatening, or require hospitalisation when, based upon appropriate medical judgement, may jeopardise the patient and may require medical or surgical intervention to prevent one of the outcomes listed in this definition. Examples of such medical events include allergic bronchospasm requiring intensive treatment in an emergency room or at home, blood dyscrasias or convulsions that do not result in inpatient hospitalisation, or the development of drug dependency or drug abuse.

The Investigator must report all SAEs, regardless of treatment group or suspected relationship to investigational medicinal product, to the Sponsor or designee **within 24 hours** of knowledge of the event.

1-Mar-2022 limab Version number: 1

The following information is the minimum that must be provided:

- Investigator/reporter's name and contact details.
- Patient identification number.
- Description of the SAE, including criteria for seriousness and initial causality assessment.

The additional information included in the SAE form must be provided to Sponsor or designee as soon as it is available. The Investigator should always provide an assessment of causality for each event reported. Upon receipt of the initial report, the Investigator's causality assessment will be requested if it was not provided with the initial report.

The procedures for completing and transmitting SAE reports are provided in Section 17.11 (Appendix 11).

8.1.3 Adverse Events of Special Interest

Adverse events of special interest, defined below, will be reported to Sponsor or designee within 24 hours of learning of the event:

- Systemic or localised allergic reactions that require immediate treatment*.
- Severe injection site reactions that last longer than 24 hours.
- Any severe or opportunistic viral, bacterial or fungal infection and/or any uncommon, unanticipated or persistent infection (viral, parasitic, bacterial, or fungal).
- Any malignancy.
- Increase in alanine transaminase (ALT) $>3 \times$ upper limit of normal (ULN); see the "Increase in ALT" flow chart in Section 17.12 (Appendix 12).

The special situations of:

- Symptomatic overdose (serious or non-serious) with IMP (any administration that is twice or more than the intended dose administered in less than 3 weeks [21 days]).
- Pregnancy discussed separately in Section 8.3.

8.1.4 Deaths

All AEs resulting in death during the study or follow-up period must be reported as SAEs irrespective of the causality, and the Investigator should supply the Sponsor and IRB/IEC if applicable, with as much detail of the events leading to death as possible immediately and any additional requested information (eg, autopsy reports and terminal medical reports).

The convention for recording death is as follows:

• AE term: lead/exact cause of death (eg, multiple organ failure, pneumonia, myocardial infarction).

^{*} In the event that a patient has a systemic allergic reaction that requires immediate treatment, blood samples should be withdrawn as soon as feasible (not to interfere with treatment of the reaction) for the analysis of ADA, serum tryptase, C1q, C1 inhibitor, C3 and C4, and repeated at 4 hours and 24 hours. Detailed instructions for sample collection, preparation and shipping will be provided in a Laboratory Manual.

Outcome: fatal.

• Causality assessment.

The only exception is if the cause of death is unknown (ie, sudden or unexplained death), in which case the AE term may be "death" or "sudden death". As many details about the fatal cases should be provided as possible and available.

1-Mar-2022

Version number: 1

8.1.5 Disease-related events and/or disease-related outcomes not qualifying as AEs or SAEs

Not applicable.

8.1.6 Regulatory reporting requirements for SAEs

Prompt notification by the Investigator to the Sponsor of an SAE is essential so that legal obligations and ethical responsibilities towards the safety of patients and the safety of a study intervention under clinical investigation are met.

The Sponsor has a legal responsibility to notify both the local regulatory authority and other regulatory agencies about the safety of a study intervention under clinical investigation. The Sponsor will comply with country-specific regulatory requirements relating to safety reporting to the regulatory authority, IRB/ IEC, and Investigators.

Serious adverse events that are considered expected will be specified in the reference safety information (specify IB or label), as applicable.

Investigator safety reports must be prepared for suspected unexpected serious adverse reactions (SUSARs) according to local regulatory requirements and Sponsor policy and forwarded to Investigators as necessary.

An Investigator who receives an Investigator safety report describing an SAE, SUSAR or any other specific safety information (eg, summary or listing of SAEs) from the Sponsor will review and then file it along with the IB and will notify the IRB/IEC, if appropriate according to local requirements. It is the responsibility of the Sponsor to assess whether an event meets the criteria for a SUSAR, and therefore, is expedited to regulatory authorities.

8.1.7 Reporting to Regulatory Authorities, IECs/IRBs and other Investigators

The Sponsor will ensure that processes are in place for submission of reports of SUSARs and special situations etc occurring during the study to the regulatory authorities, IECs/IRBs and other Investigators concerned by the investigational medicinal product, as applicable. Reporting will be performed by the Investigator or the Sponsor (or designee) in accordance with the applicable regulatory requirements.

Details of procedures and responsibilities will be documented in a Safety/SAE management plan for the study.

8.2 Emergency Procedures

Each patient will be given an emergency card at the enrolment/randomisation visit and asked to carry it with them at all times in case of an emergency. The card will include the following study information as a minimum: a patient identifier, investigational drug name and name and 24-hour telephone number of the Investigator (or medically qualified designee). Patients should be asked to destroy this card at the end of the study.

1-Mar-2022

Version number: 1

If the Investigator needs urgent advice regarding the management of an SAE or any other safety issue, an 'on call' contracted medical advisor is available 24 hours a day by telephone, as per the details below.

Emergency contact for medical monitor is specified in the STUDY PERSONNEL section.

8.2.1 Emergency Treatment Code-break

The IRT will be programmed with blind-breaking instructions. In case of an emergency, the Investigator has the sole responsibility for determining if unblinding of a participant's intervention assignment is warranted (eg, in case of available antidote). Participant safety must always be the first consideration in making such a determination. If the Investigator decides that unblinding is warranted, he/she may, at his/her discretion, contact the Sponsor to discuss the situation prior to unblinding a participant's intervention assignment unless this could delay emergency treatment of the participant. If a participant's intervention assignment is unblinded, the Sponsor must be notified within 24 hours after breaking the blind. The date and reason that the blind was broken must be recorded in the source documentation and case report form, as applicable. If the code is broken upon Investigator's request, the participant must withdraw from IMP administration and the patient should return for a final study assessment (see Section 9.2).

8.3 Pregnancy

8.3.1 Maternal Exposure

If a patient becomes pregnant during the study, IMP should be discontinued immediately.

Although pregnancy is not considered an AE it does require reporting expeditiously with follow-up to an outcome, for up to 6 months post-partum, for mother and infant. If any study patient is found to be pregnant while enrolled in the study, the Investigator must submit a pregnancy report form within 24 hours of becoming aware of confirmation of the pregnancy (see Section 17.10 - Appendix 10 for a flow chart of the process).

Any event of pregnancy that occurs during the study (including long-term follow-up) or up to 5 months following the last dose of IMP will be reported. Abnormal pregnancy outcomes (eg, spontaneous abortion, fetal death, stillbirth, congenital anomalies, ectopic pregnancy) are considered SAEs and will be reported as such.

A follow-up report will be provided once the outcome of the pregnancy is definitive and the partner has given consent using a form approved by the relevant IEC for her personal medical information to be discussed, if applicable. Follow-up of offspring for 6 months is desirable. In the event of any abnormality, the neonate will also be followed up if there is parental consent in place for such information to be discussed.

8.3.2 Paternal Exposure

Pregnancy of a patient's partner is not considered to be an AE. However, any conception occurring from the date of dosing until 5 months after last dosing will be reported within 24 hours on pregnancy report form and followed up for its outcome.

9 WITHDRAWAL OF PATIENTS FROM TREATMENT AND/OR THE STUDY

Patients are free to withdraw from participation in the study at any time, without prejudice to their further care. In some circumstances, patients may be discontinued from study treatment but continue certain study assessments.

The Investigator should discontinue study treatment for a given patient if, on balance, he/she believes that continuation would be detrimental to the patient's well-being.

Study treatment will be discontinued and/or patients may be withdrawn from the study under the following circumstances:

- 1. Withdrawal of consent.
- 2. Severe noncompliance with the protocol as judged by the Investigator and/or the Sponsor.
- 3. Patients incorrectly initiated on study treatment (eg, patient has been determined to have met one or more of the exclusion criteria for study participation at study entry and continuing study treatment might constitute a safety risk).
- 4. AEs that, in the opinion of the Investigator or the Medical Monitor, contraindicate further dosing.
- 5. Pregnancy.
- 6. Disease progression in the investigator's point of view.
- 7. Study terminated by the Sponsor. This includes any decision on study termination after IDMC recommendation. The IDMC reviews and evaluates accumulating blinded and unblinded if deemed necessary safety and efficacy data (including by treatment arm or patient) to ensure the safety of trial subjects (please refer to Section 3.8 of the protocol).
- 8. Lost to follow-up.

9.1 Discontinuation of the Patient from Investigational Medicinal Product

9.1.1 Reasons for Permanent Discontinuation of Investigational Medicinal Product

The IMP will be permanently discontinued for any of the following reasons:

- 1. Anaphylactic reaction or other severe systemic reaction to the IMP injection.
- 2. Diagnosis of a malignancy during the study.
- 3. Major surgery.
- 4. Severe intercurrent illness.
- 5. Evidence of confirmed pregnancy.

6. Any infection that is opportunistic, such as active TB, non-tuberculous mycobacterial infections and other infections whose nature or course may suggest an immunocompromised status.

1-Mar-2022

Version number: 1

- 7. Severe laboratory abnormalities:
 - Absolute neutrophil count $\leq 0.5 \times 10^9 / L$;
 - Platelet count $\leq 50 \times 10^9 / L$;
 - Serum ALT >3 ULN and Total Bilirubin >2 ULN;
 - Serum ALT >5 ULN if baseline ALT ≤2 ULN or ALT >8 ULN if baseline ALT >2 ULN.

Note: If the laboratory abnormality is considered causally related to the IMP, the IMP will be permanently discontinued. In cases where a causal relationship to the IMP can be reasonably excluded (ie, an alternative cause is evident), the IMP will be discontinued but it may be resumed when the laboratory abnormality is sufficiently normalised.

8. If a subject experiences an adverse event assessed as ≥ Grade 3 CTCAE [severe; see Section 8.1.1.1] (or ≥ Grade 2 CTCAE [moderate; see Section 8.1.1.1] for the System Organ Classes of Cardiac disorders and Blood and Lymphatic disorders) per CTCAE v5.0, the subject should be discontinued from further dosing. Such subjects should not be discontinued from the study, but they should be monitored by their medical practitioner and study investigator until the adverse event (AE) resolves or stabilizes.

Other reasons that may lead to the permanent discontinuation of IMP include:

- Treatment with any prohibited systemic concomitant medication or procedure (see Section 5.3.2 and Section 5.3.4).
- Treatment with any topical concomitant rescue therapy in the first 14 days from Baseline (see Section 5.3.4).
- After Day 14, treatment with topical concomitant rescue therapy on more than
 2 occasions during study participation. The maximum permitted duration of topical
 concomitant rescue therapy on either occasion is 2 consecutive weeks. If duration of
 treatment is exceeded on either occasion this will also lead to permanent
 discontinuation of IMP.

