9.1.2 Reasons for Temporary Discontinuation of Investigational Medicinal Product

Dosing of IMP should be temporarily interrupted for the following reasons:

- 1. Clinically important laboratory abnormalities, such as:
 - Absolute neutrophil count $\leq 1.0 \times 10^9 / L$ but $> 0.5 \times 10^9 / L$;
 - Platelet count $\leq 100 \times 10^9 / L$ but $> 50 \times 10^9 / L$;
 - Creatine phosphokinase $>10 \times ULN$.
- 2. Other intercurrent illness.
- 3. An infection requiring systemic treatment with antibiotic, antifungal, antiviral, antiparasitic or antiprotozoal agents, or requiring oral treatment with such agents for more than 2 weeks.

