9.1.2.1 Re-challenge

Reinitiation of intervention with the IMP will be done under close and appropriate clinical and/or laboratory monitoring once the Investigator will have considered according to his/her best medical judgment that the responsibility of the IMP(s) in the occurrence of the concerned adverse event was unlikely and if the selection criteria for the study are still met (refer to Section 4).

If there is to be a delay to any dosing of IMP outside of the permitted visit windows as per the Schedule of Assessments (Section 6.1), the Investigator must consult with, and receive written confirmation that dosing can be rescheduled from, the Medical Monitor.

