9.1.2.1.1 Study intervention restart or rechallenge after liver stopping criteria met

Study intervention restart or rechallenge after liver chemistry stopping criteria are met by any participant in this study is not allowed.

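### Where an alternative cause is evident, the Note to Protocol 9.1.1 item 7 lets IMP resume after the two ALT criteria, while 9.1.2.1.1 bans any restart after liver stopping criteria

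*Protocol*

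**What the plan says.** Section 9.1.1 lists reasons for stopping IMP permanently. Item 7 covers severe laboratory abnormalities and has four bullets: low neutrophils, low platelets, "Serum ALT >3 ULN and Total Bilirubin >2 ULN", and ALT alone above 5 ULN (above 8 ULN if baseline ALT exceeds 2 ULN).

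The Note under item 7 splits these by causality. If the abnormality is related to IMP, the stop is permanent. The other branch opens "In cases where a causal relationship to the IMP can be reasonably excluded (ie, an alternative cause is evident") and continues "the IMP will be discontinued but it may be resumed when the laboratory abnormality is sufficiently normalised". It applies to all four bullets.

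Section 9.1.2.1.1 reads: "Study intervention restart or rechallenge after liver chemistry stopping criteria are met by any participant in this study is not allowed". It has no causality exception. It is numbered under 9.1.2, the temporary-interruption section, whose list contains no liver criterion.

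Three other provisions bear on the point:

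- **Item 8 of 9.1.1.** For an adverse event of CTCAE Grade 3 or above (Grade 2 or above for cardiac and for blood and lymphatic disorders), "the subject should be discontinued from further dosing". It has no causality exception.
- **Section 9.1.2.1 (Re-challenge).** The investigator must judge IMP responsibility unlikely, and the selection criteria must still be met. A dose outside the visit window needs the Medical Monitor's written confirmation.
- **Section 8.1.3.** ALT above 3 ULN is an adverse event of special interest and "will be reported to Sponsor or designee within 24 hours of learning of the event".

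**The concern.** The same patient gets opposite answers depending on which section the site opens. A site handling an item 7 event works from 9.1.1, where the Note says resumption is possible and nothing points to the ban. A site that acts on the Note in good faith could re-dose a patient whom 9.1.2.1.1 says must not be restarted. That includes a patient who met the combined ALT and bilirubin criterion. What is at stake is participant safety and an avoidable protocol deviation. Section 12.3 rules out sponsor waivers, so case-by-case clearance is not a remedy.

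**Working it through.** No arithmetic in the plan is at issue. The check is to take one case through each rule.

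**Which criteria does the ban cover?** The readable text does not define liver chemistry stopping criteria. The item 7 ALT bullets are the only liver thresholds there that require IMP to stop; ALT above 3 ULN alone triggers reporting. The surviving text of Appendix 12 mentions discontinuation decisions but gives no other stopping threshold and no restart rule. Equating the item 7 ALT bullets with the stopping criteria is therefore an inference, though the natural one.

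**Can ALT normalise before the next dose?** Doses after Day 1 are scheduled 28 days apart, each with a window of ±3 days. Consecutive in-window doses can therefore be 28 − 6 = 22 to 28 + 6 = 34 days apart. Safety bloods are taken before the injection on dosing days (Tables 6-1 to 6-3) and are evaluated centrally (Section 6.4.4). A result may therefore arrive after that day's dose, leaving about four weeks to the next one. Appendix 12 counts ALT as normalised at or below ULN, or at the baseline value if that was above ULN.

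**Illustrative case.** Baseline ALT is at most 2 ULN. The Day 57 sample shows ALT above 5 ULN. An alternative cause is established: for example muscular injury, which Appendix 12 asks sites to rule out, or hepatitis A, for which it requests a test. ALT is normal by the Day 85 window (Days 82 to 88).

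| Rule | Result for this case |
|---|---|
| 9.1.1 item 7 Note | IMP may be resumed |
| 9.1.2.1, causality | Met: IMP responsibility unlikely |
| 9.1.2.1, selection criteria | Not failed on exclusion criterion 7, which names HIV and hepatitis B and C |
| 9.1.2.1, Medical Monitor confirmation | Not triggered: the dose is inside the window |
| 9.1.1 item 8 | Stops dosing only if an adverse event is assessed as Grade 3 or above |
| 9.1.2.1.1 | Restart not allowed |

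If item 8 does not apply, the first and last rows conflict. The same holds for ALT above 3 ULN with bilirubin above 2 ULN.

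**Where there is no conflict with 9.1.2.1.1.** In the related branch, both provisions keep the patient off IMP. For neutrophils and platelets, the ban does not apply because it concerns liver criteria only.

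**The case against.** The strongest reply is that both rules can be obeyed at once. The Note is permissive, the ban is specific and absolute, and it sits directly below the restart procedure, so a site that does not restart complies with both. That is correct, and it is how the text should be read. But the protocol does not say which provision prevails, and the Note is itself specific, because it is attached to the ALT bullets.

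The second reply is that few patients, if any, are left. Item 7 is headed as severe abnormalities, and Section 8.1.1.1 equates severe with Grade 3 or above. If every item 7 ALT event is recorded as an adverse event of that grade, item 8 ends dosing. This narrows the group, but a heading is not a grading, and the documents give no ALT cut-offs for the CTCAE grades. The restart conditions in 9.1.2.1 narrow it further: hepatitis B or C positivity would fail the selection criteria, and a late dose needs written confirmation. Neither stops the case above. Expedited reporting, and the Appendix 12 step that informs the Site Monitor and through them the Study Manager, alert the sponsor but do not themselves bar re-dosing.

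The third reply, that the Appendix 12 chart may settle the matter, cannot be tested because the chart is not shown.

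A reader might infer more: that the protocol allows rechallenge after drug-related liver injury, that restart after liver events is uncontrolled, or that trial results are affected. The documents support none of these. The Note stops IMP permanently in related cases, the controls above exist, and no endpoint, analysis set or power figure depends on this rule.

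**Conclusion.** The inconsistency is real and narrow. It is confined to the two ALT criteria, to cases where a causal relationship is reasonably excluded, and to events not already stopped by item 8 or by the checks in 9.1.2.1. The clearest exposed case is an ALT event that normalises before the next scheduled dose, from a cause that does not fail the selection criteria. The documents give no event rate, so the number of patients cannot be estimated; it is probably small.

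The conclusion assumes that the item 7 ALT bullets are the liver chemistry stopping criteria meant in 9.1.2.1.1. If the Appendix 12 chart defines them differently, the overlap could change. Confidence is medium for that reason. The point should be fixed because it concerns re-exposure after a liver-safety stop and the correction is cheap.

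**What to change.** - In the Note to 9.1.1 item 7, limit the resumption sentence to the neutrophil and platelet criteria and make it subject to item 8. Otherwise the Note would still permit resumption after a blood and lymphatic adverse event of Grade 2 or above, where item 8 stops dosing.
- Add to the Note: *For the ALT criteria, restart is not allowed; see Section 9.1.2.1.1.*
- In 9.1.2.1.1, name the ALT criteria of 9.1.1 item 7.
- Check that the Appendix 12 flow chart agrees, and notify sites.

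This adopts the stricter rule already written. A causality exception in 9.1.2.1.1 would also remove the conflict, but it would relax a safety ban and need its own justification.

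**Cost.** A few sentences in a protocol amendment, with whatever approvals Section 12.3 requires, and a site letter. Whether the amendment is substantial is for the sponsor to decide. The letter can state at once that 9.1.2.1.1 governs.

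**Downside.** Patients with a clear non-drug cause cannot resume IMP, as 9.1.2.1.1 already requires. Under 9.1.3, those stopped permanently in the first study period also lose eligibility for the second period and for the LTE at Day 169.
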